### 9.3.2 Pharmacokinetic Statistical Methodology

Pharmacokinetic parameters will be evaluated to estimate drug interaction for dabigatran and rosuvastatin with lasmiditan. Log-transformed  $C_{\max}$  and  $AUC(0-\infty)$  parameters for dabigatran and rosuvastatin will be analyzed using a mixed effects linear model to compare dabigatran and rosuvastatin administered alone (reference), and dabigatran and rosuvastatin administered with lasmiditan (test). The model will include a fixed effect for treatment and a random effect for participant. The least squares (LS) means for each treatment, the difference between the treatment LS means ( $[\text{dabigatran or rosuvastatin + lasmiditan}] - \text{dabigatran or rosuvastatin alone}$ ), and the associated 90% CIs will be estimated from the model and back-transformed from the log scale to provide estimates of the geometric means, geometric mean ratio, and corresponding 90% CIs.

Example of the SAS code for the analysis:

```
proc mixed data=xxx alpha=0.1;
  class treat subjid;
  model log_pk = treat / residual ddfm=kr;
  random subjid;
  lsmeans treat / cl pdiff alpha=0.1;
  ods output lsmeans=lsm01 diffs=estims01;
run;
```

The  $t_{\max}$  will be analyzed non-parametrically using a Wilcoxon signed rank test. Estimates of the median difference, comparing dabigatran or rosuvastatin + lasmiditan (test) – dabigatran or rosuvastatin alone (reference), and the corresponding 90% CIs for the difference between treatments will be calculated and presented, alongside the p-value from the Wilcoxon signed-rank test.

Example SAS code to be used for the Wilcoxon signed-rank test:

```
proc univariate data = xxx cipctldf(alpha = 0.1);
  var ref test diff;
  ods output quantiles = quant01;
  ods output testsforlocation = out01;
run;
```

The effect of polymorphisms in genes coding for certain transporters (e.g., ABCG2, ABCB1, ABCC2, SLCO1B3, NTCP, and SLCO2B1) on the magnitude of the interaction between rosuvastatin and lasmiditan may be explored. For each participant, the ratio of rosuvastatin exposures with and without concomitant lasmiditan exposures will be calculated. A graphical

---

analysis of these ratios between participants with and without single nucleotide polymorphism (SNPs) of interest is intended.

Additional analyses may be conducted as warranted.

## **9.4 Safety and Tolerability Assessments**

### **9.4.1 Adverse events**

Where changes in severity are recorded in the Case Report Form (CRF), each separate severity of the adverse event (AE) will be reported in the listings, only the most severe will be used in the summary tables. A pre-existing condition is defined as an AE that starts before the participant has provided written informed consent and is ongoing at consent. A non-treatment emergent AE is defined as an AE which starts after informed consent but prior to dosing. A TEAE is defined as an AE which occurs postdose or which is present prior to dosing and becomes more severe postdose.

All AEs will be listed. TEAEs will be summarized by treatment, severity and relationship to the study drug. The frequency (the number of AEs, the number of participants experiencing an AE and the percentage of participants experiencing an AE) of TEAEs will be summarized by treatment, Medical Dictionary for Regulatory Activities (MedDRA) Version 23.1 system organ class and preferred term. The summary and frequency TEAE tables will be presented for all causalities and those considered related to the study drug by the investigator. Any serious AEs will be listed. AEs by day of onset will be presented.

Discontinuations due to AEs will be listed.

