4.2. Scientific Rationale for Study Design

The study has an open-label, fixed-sequence, 2-part design in which each subject receives either dabigatran etexilate or rosuvastatin alone (Parts 1 and 2, respectively), and lasmiditan alone for 2 consecutive days followed by lasmiditan co-administered with either dabigatran etexilate or rosuvastatin, allowing each subject to act as his/her own control for safety and PK comparisons. The washout period between dabigatran etexilate or rosuvastatin doses of 7 days is considered sufficient based on the half-life of dabigatran of 12 to 17 hours, and the half-life of rosuvastatin of approximately 19 hours. A 200-mg dose of lasmiditan was selected as it is the highest potential recommended dose for lasmiditan. Data from multiple doses of lasmiditan demonstrated that steady state was achieved by 48 hours after dose with no accumulation with once-daily dosing. Given that patients may take lasmiditan on consecutive days, 3-day dosing with lasmiditan is deemed to be appropriate.

Human BCRP (encoded by the gene ABCG2) is polymorphic. Participants with the c.421C>A and c.34G>A polymorphisms, specifically the c.34AA, c.421AA, and c.34GA/421CA genotypes, will be excluded because these genetic polymorphisms are associated with impaired BCRP activity (Furukawa et al. 2009; Keskitalo et al. 2009; Wan et al. 2015). Because the activity of BCRP is impaired with these participants, it would be anticipated that even complete inhibition of BCRP would not result in a substantial change in rosuvastatin exposure. Accordingly, excluding participants with these polymorphisms will ensure that the “worst-case” interaction between lasmiditan and rosuvastatin will be evaluated in this study.

The human organic anion-transporting polypeptide 1B1 (OATP1B1) transporter (also known as SLCO1B1) is also polymorphic. To evaluate worst-case interactions between lasmiditan and rosuvastatin, participants with the c.521TC or c.521CC polymorphisms will be excluded from this study because these genetic polymorphisms are associated with decreased transporting activity of OATP1B1 (Niemi et al. 2011) and higher plasma rosuvastatin concentrations (Crestor Prescribing Information, 2020).

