#### **4.2 Secondary Objectives**

The secondary objectives of the study are:

- To evaluate the safety and tolerability of dabigatran etexilate or rosuvastatin in combination with lasmiditan in healthy participants
- To evaluate the pharmacokinetics of lasmiditan and M8

[figure not shown]
The secondary endpoints of the study are:

- A summary of the number of treatment-emergent adverse events (TEAEs) and serious adverse events (SAE)
- $C_{max}$  of lasmiditan and M8
- Time of maximum observed drug concentration ( $t_{max}$ ) of lasmiditan and M8
- AUC (0- $\infty$ ) of lasmiditan and M8

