**Figure 1 – General schema for LAIO**

## 6. TREATMENTS

The following is a list of the study treatment abbreviations that will be used in the TFLs.

Part	Day	Study Treatment Name	Treatment order in TFL
1	1	150 mg dabigatran etexilate	1
	8-9	200 mg lasmiditan	2
	10	150 mg dabigatran etexilate + 200 mg lasmiditan	3
2	1	10 mg rosuvastatin	4
	8-9	200 mg lasmiditan	5
	10	10 mg rosuvastatin + 200 mg lasmiditan	6

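### TEAE tables set two pooled lasmiditan-alone doses (Days 8-9) beside one combination dose (Day 10), with no rule assigning events to treatments, so this pair of columns is not like for like

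*SAP*

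**What the plan says.** - **Treatment labels.** SAP Section 6 opens: "The following is a list of the study treatment abbreviations that will be used in the TFLs". Each part has three labels: the probe drug alone (dabigatran etexilate or rosuvastatin) on Day 1, "200 mg lasmiditan" on Days 8-9 as a single row, and the combination on Day 10. Protocol 6.1.1 confirms one lasmiditan dose on each of Days 8 and 9 and one combined administration on Day 10.
- **Tabulation.** SAP 9.4.1 states: "TEAEs will be summarized by treatment, severity and relationship to the study drug". The frequency tables, also by treatment, give "the number of AEs, the number of participants experiencing an AE and the percentage of participants experiencing an AE".
- **Definition.** "A TEAE is defined as an AE which occurs postdose or which is present prior to dosing and becomes more severe postdose". This sets no end to the period after a dose and does not tie an event to one of several successive doses.
- **Other AE output.** "AEs by day of onset will be presented". All AEs, and discontinuations due to AEs, are listed.
- **Collection.** Under Protocol 8.3.1, AE collection ends at the follow-up visit, which the Schedule of Activities places on Day 16, plus or minus 1 day.
- **Purpose.** The secondary objective in SAP 4.2 is the safety and tolerability of the probe combined with lasmiditan, and its endpoint is a summary count of TEAEs and SAEs. Protocol 4.2 presents the fixed sequence as "allowing each subject to act as his/her own control for safety and PK comparisons".

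**The concern.** Protocol 2.3 reports that lasmiditan itself commonly causes dizziness, fatigue, paresthesia and sedation. A reader asking whether adding the probe worsens tolerability will therefore look from the combination column to the lasmiditan-alone column. Those two columns differ in number of doses and, under the usual attribution, in days of observation. The table could make the combination look better tolerated than lasmiditan alone, or hide a modest excess, because of how the columns are built. The SAP gives no window, exposure adjustment or column denominator that would let the reader correct for this.

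**Working it through.** The plan states no figure for TEAEs. Its only stated calculation is the power of the PK equivalence tests, which does not bear on this point.

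**1. Exposure per column.** The SAP gives no attribution rule, so assume that an event belongs to the most recent dose. Dosing days come from SAP Section 6, and the follow-up day and enrolment from the Protocol (Schedule of Activities and 4.1.1).

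| Column | Doses | Days | Part 1 participant-days (72 enrolled) | Part 2 participant-days (32 enrolled) |
|---|---|---|---|---|
| Probe alone | 1 | Day 1 to 8 = 7 | 504 | 224 |
| Lasmiditan alone | 2 | Day 8 to 10 = 2 | 144 | 64 |
| Combination | 1 | Day 10 to 16 = 6 (5 to 7) | 432 | 192 |

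The lasmiditan column has twice the doses and one third of the days of the combination column.

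**2. Expected events when nothing differs.** Let p be the acute event risk per lasmiditan dose and b the background events per day, both the same with and without the probe. The documents give neither, so both are assumptions.

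- Lasmiditan alone: 2p + 2b per participant.
- Combination: p + 6b per participant.
- With b = 0, the ratio of combination to lasmiditan alone is p/2p = 0.50, whatever p is and however correlated the doses are within a person.
- The counts are equal when 2p + 2b = p + 6b, that is p = 4b. With follow-up at 5 or 7 days, the balance point is p = 3b or p = 5b.

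| p | b | Lasmiditan alone | Combination | Ratio |
|---|---|---|---|---|
| 0.20 | 0 | 0.40 | 0.20 | 0.50 |
| 0.20 | 0.02 | 0.44 | 0.32 | 0.73 |
| 0.05 | 0.03 | 0.16 | 0.23 | 1.44 |

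**3. Percentage of participants affected.** With b = 0 and independent doses, lasmiditan alone gives 1 - (1 - p)², against p for the combination:

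- p = 0.10: 19% v 10%
- p = 0.20: 36% v 20%
- p = 0.30: 51% v 30%

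For the two percentages to look the same, the combination would need a true per-dose risk ratio of (1 - (1 - p)²)/p = 2 - p. That is 1.9 at p = 0.10 and 1.6 at p = 0.40. If the same people react to every dose, the percentages are equal and only the event counts are distorted.

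**4. Effect of re-tabulating.** Splitting Days 8 and 9 gives p + b, p + b and p + 6b for Days 8, 9 and 10. The doses then match but the days do not. Adding an equal 24-hour window gives p + b in all three columns, a ratio of 1.0 when nothing differs.

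**The case against.** The strongest reply is that the SAP never sets these two columns against each other. The endpoint is a descriptive count, with no contrast or test, and the objective names no comparator. The PK reference is the probe alone, and for that pair the windows are similar (one probe dose each, 7 days against about 6). This stands: the problem concerns one pair of columns and does not reach every TEAE count.

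Second, output by day of onset is already promised and can separate Days 8, 9, 10 and later. This stands in part. The sentence gives no denominator, post-dose window or preferred-term breakdown, and the TFL shells are a separate document not available here.

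Third, the 6-day window is inferred. That is correct, and the missing assignment rule is the firmer gap.

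Three stronger readings are tempting, and the documents do not support them:

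- *That the direction is shown to reverse, for instance at p = 0.20 and b = 0.05.* With 6 elapsed days this is a tie: 0.40 + 0.10 = 0.50 against 0.20 + 0.30 = 0.50. A reversal needs b above p/4, and neither rate is known.
- *That the own-control safety comparison in Protocol 4.2 is defeated.* That sentence names no single comparator, and the probe-alone comparison is largely intact.
- *That re-tabulation would remove run-in selection.* Anyone who stops after Day 8 or 9 never receives the combination. That follows from the fixed sequence, and no table cures it. Protocol 7.2 expects discontinuation to be uncommon, and discontinuations due to AEs are listed.

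**Conclusion.** The point holds for lasmiditan alone against the combination. Two doses share one label, the comparator is a single dose, and no rule assigns events to the successive treatments. Under most-recent-dose attribution the imbalance is 2 doses in 2 days against 1 dose in about 6 days. If events are mainly acute and dose-related, the combination column shows as little as half the events of lasmiditan alone when nothing differs. Background events work against this, so the net direction depends on rates that the documents do not give. The matter is confined to the presentation of a secondary, descriptive endpoint. The primary PK analysis, sample size and data collection are unaffected. It is a cheap improvement to the tables; the safety evaluation does not fail without it.

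**What to change.** In SAP Sections 6 and 9.4.1 and the TFL shells:

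1. State the rule that assigns an AE to a treatment, for example the most recent dose before onset.
2. Show Day 8 and Day 9 as separate columns in the TEAE frequency tables.
3. Add one TEAE table per part by dosing day (Days 1, 8, 9 and 10) over an equal post-dose window, with participants dosed that day as the denominator. Use 0-24 h, or the calendar day of dosing if onset clock time is not recorded; the documents do not say whether it is. Calendar days are close to equal windows, because Protocol 4.3 has doses given at about the same time each treatment day.
4. Keep the all-onset table as the endpoint table. The stated half-lives are 12 to 17 hours for dabigatran and about 19 hours for rosuvastatin, so 24 hours spans only about 1.3 (24/19) to 2 (24/12) half-lives and later events must not be lost.

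The cost is SAP and shell wording plus one extra table per part. Dosing dates and times are already recorded (Protocol 6.4 and 9.3.3), and no visit, sample or participant is added. The downside is that the new table omits events after 24 hours.

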### **9.4.2 Concomitant medication**

Concomitant medication will be coded using the WHO drug dictionary (Version WHODD SEP20B3). Concomitant medication will be listed.

### **9.4.3 Clinical laboratory parameters**

All clinical chemistry, hematology, and coagulation data will be summarized by part and parameter, and listed. Urinalysis data will be listed only. Additionally, clinical chemistry, hematology, coagulation, and urinalysis data outside the reference ranges will be listed and flagged on individual participant data listings.

### **9.4.4 Vital signs**

Vital signs data will be summarized by part together with changes from baseline, where baseline is defined as the predose assessment of each dosing period (Day 1 for period 1 and Day 10 for Period 2). Figures of mean vital signs and mean changes from baseline profiles will be presented by treatment.

Values for individual participants will be listed.

#### **9.4.5    Electrocardiogram (ECG)**

ECGs will be performed for safety monitoring purposes only and will not be presented. Any clinically significant findings from ECGs will be reported as an AE.

#### **9.4.6    Hepatic Monitoring**

If a participant experiences elevated alanine aminotransferase (ALT)  $\geq 3 \times$  upper limit of normal (ULN), alkaline phosphatase (ALP)  $\geq 2 \times$  ULN, or elevated total bilirubin (TBL)  $\geq 2 \times$  ULN, liver tests will be performed to confirm the abnormality. Additional safety data may be collected if required, as defined in the protocol. Where applicable, the following will be presented.

The participants' liver disease history and associated person liver disease history data will be listed. Any concomitant medications that have potential for hepatotoxicity, including acetaminophen will be listed. Results from any hepatic monitoring procedures, such as a magnetic resonance elastography (MRE) scan, and biopsy assessments will be listed, if performed.

Hepatic risk factor assessment data will be listed. Liver related signs and symptoms data will be summarized by treatment and listed. Alcohol and recreational drug use data will also be listed.

All hepatic chemistry, hematology, coagulation, and serology data will be listed. Values outside the reference ranges will be flagged on the individual participant data listings.

#### **9.4.7    Columbia-Suicide Severity Rating Scale (C-SSRS) / Self-Harm Supplement**

All C-SSRS and Self Harm Supplement data will be listed.

#### **9.4.8    Other assessments**

All other safety assessments not detailed in this section will be listed but not summarized or statistically analyzed.

### **10.    INTERIM ANALYSES**

No interim statistical analyses are planned.

### **11.    CHANGES FROM THE PROTOCOL SPECIFIED STATISTICAL ANALYSES**

There were no changes from the protocol specified statistical analyses.

## **13. DATA PRESENTATION**

### **13.1 Derived Parameters**

Individual derived parameters (e.g. PK parameters) and appropriate summary statistics will be reported to three significant figures. Observed concentration data, e.g.  $C_{max}$ , should be reported as received. Observed time data, e.g.  $t_{max}$ , should be reported as received. N and percentage values should be reported as whole numbers. Median values should be treated as an observed parameter and reported to the same number of decimal places as minimum and maximum values.

### **13.2 Missing Data**

Missing data will not be displayed in listings.

### **13.3 Insufficient Data for Presentation**

Some of the TFLs may not have sufficient numbers of participants or data for presentation. If this occurs, the blank TFL shell will be presented with a message printed in the center of the table, such as, "No serious adverse events occurred for this study."

Leo Document ID = 9e6ed614-1151-4314-90c6-1a23104322e5

Approver: PPD

Approval Date & Time: 02-Nov-2020 13:16:21 GMT

Signature meaning: Approved

Approver: PPD

Approval Date & Time: 02-Nov-2020 15:22:28 GMT

Signature meaning: Approved

Approver: PPD

Approval Date & Time: 03-Nov-2020 10:14:37 GMT

Signature meaning: Approved

Approver: PPD

Approval Date & Time: 03-Nov-2020 11:51:39 GMT

Signature meaning: Approved
